7.2.2 Safety and tolerability assessment

Safety and tolerability assessments will include adverse event reporting and changes from baseline in laboratory parameters and vital signs. Tolerability will be assessed by the incidence of AEs leading to study drug delay or discontinuation. Safety will be monitored by assessing the procedures listed below as well as collecting of the adverse events at every visit. For details on AE collection and reporting, refer to Section 8.

7.2.2.1 Physical examination

A complete physical examination must be performed as indicated in **Table 7**.

Physical examination will be performed on the scheduled day, even if study treatment is being withheld. More frequent examinations may be performed at the discretion of the Investigator and if medically indicated.

A complete physical examination will include the examination of general appearance, skin, neck (including thyroid), eyes, ears, nose, throat, lungs, heart, abdomen, back, lymph nodes, extremities, vascular and neurological. If indicated based on medical history and/or symptoms, rectal, external genitalia, breast, and pelvic exams will be performed.

Information about the physical examination must be present in source documentation at the study site. Significant findings that are present prior to signing of informed consent form for the study must be included in the Relevant Medical History/Current Medical Conditions page on the patient's eCRF. Significant new findings that begin or worsen after informed consent for the study must be recorded on the AE eCRF.

7.2.2.2 Vital signs

Vital signs (body temperature, pulse rate, blood pressure) must be performed in the same position, either sitting or supine, before dosing and as indicated in **Table 7**.

Vital signs should be assessed on the scheduled day, even if study treatment is being withheld. More frequent examinations may be performed at the discretion of the Investigator and if medically indicated.

7.2.2.3 Height and weight

Weight will be measured as indicated in **Table 7**. Height will be collected at screening only. More frequent examinations may be performed at the discretion of the Investigator and if medically indicated.

7.2.2.4 Performance status

The ECOG performance status will be assessed as indicated in **Table 8**.

Assessments of performance status will be performed on the scheduled day, even if study treatment is being withheld.

Table 8: ECOG performance status

Grade	ECOG Status
0	Fully active, able to carry on all pre-disease performance without restriction
1	Restricted in physically strenuous activity but ambulatory and able to carry out work of a light or sedentary nature (e.g., light house work, office work)
2	Ambulatory and capable of all self-care but unable to carry out any work activities. Up and about more than 50% of waking hours
3	Capable of only limited self-care, confined to bed or chair more than 50% of waking hours
4	Completely disabled. Cannot carry on any self-care. Totally confined to bed or chair

7.2.2.5 Ophthalmologic assessments

Ophthalmologic examination will be performed as indicated in **Table 7** which includes: visual acuity testing, slit lamp examination of the anterior eye segment, IOP, and fundoscopy. Additional examination methods such as specular microscopy (that enables a magnified, direct view of the corneal epithelium), corneal pachymetry, and dilated fundoscopy will be performed as clinically indicated.

7.2.2.6 Laboratory evaluations

Clinical laboratory analyses are to be performed by the local laboratory as indicated in **Table 7** and **Table 9**. Laboratory tests will be collected and analyzed on the scheduled day, even if study treatment is being withheld. More frequent assessments may be performed at the discretion of the Investigator and if medically indicated and should be recorded on the Unscheduled Visit eCRFs.

At any time during the study, abnormal laboratory parameters which are clinically relevant (e.g., require dose modification and/or interruption of study treatment, lead to clinical symptoms or signs, or require

therapeutic intervention), whether specifically requested in the protocol or not, will be recorded on the Adverse Events eCRF page. Laboratory data will be summarized using the CTCAE (version 5.0).

The Ohio State University Multi-Site Clinical Trial Team must be provided with a copy of the laboratory's certification, and normal ranges for each parameter measured. In addition, if at any time a patient has laboratory parameters obtained from a different outside laboratory, a copy of the certification and normal ranges for that laboratory will be required.

Hematology

Hematology tests are to be performed by the local laboratory according to the visit schedule outlined in **Table 7**. For details on the hematology panel refer to **Table 9**.

Clinical chemistry

Clinical chemistry tests are to be performed by the local laboratory according to the visit schedule outlined in **Table 7**. For details on the biochemistry panel refer to **Table 9**.

Coagulation

International normalized INR, pro-thrombin time (PT), partial thromboplastin time will be measured according to the visit schedule in **Table 7** and **Table 9**.

Urinalysis

Urinalysis includes dipstick analysis will be performed according to the visit schedule in **Table 7** and **Table 9**. Microscopic urinalysis will be performed only if macroscopic urinalysis result is abnormal.

Pregnancy and assessments of fertility

All WOCBP (pre-menopausal or less than 1 year after the onset of menopause) must have a serum pregnancy test (β -hCG) \leq 72 hours before the first dose of study treatment. Additionally, a serum pregnancy test should be performed at Day 1 of each cycle and at the End of Treatment visit.

Table 9: Clinical laboratory parameters collection plan

Test Category	Test Name
Hematology	Hematocrit, Hemoglobin, Red blood cell count, Platelets, White blood cells, Differential (Basophils, Eosinophils, Lymphocytes, Monocytes, Neutrophils)
Biochemistry	Albumin, Alkaline phosphatase, ALT (SGPT), AST (SGOT), Calcium (can be corrected), Chloride, Creatinine, Blood Urea Nitrogen (BUN), Potassium, Sodium, Magnesium, Phosphate. Direct Bilirubin, Indirect Bilirubin, Total Bilirubin, Lipid profile (Total Cholesterol, Triglycerides), Total Protein, Urea, Uric Acid, Amylase, Lipase
Urinalysis	Macroscopic Panel (Dipstick) (Blood, Glucose, Ketones, pH, Protein, Specific Gravity). Microscopic Panel (Red Blood Cells, WBC)
Coagulation	Prothrombin time (PT) or International normalized ratio [INR]), Partial thromboplastin time (PTT)

Pregnancy Test	Serum hCG at screening; day 1 of each cycle, EOT and other times points
----------------	---

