1.2.1.2.3 Clinical pharmacokinetics

The pharmacokinetics (PK) of Infigratinib and active metabolites have been evaluated following single and repeat daily doses in the ongoing phase I study (CInfigratinibX2101).

At 5 and 10 mg/day, plasma concentrations were low and frequently below the lower limit of quantification. Plasma concentrations were consistently quantifiable starting at 20 mg/day.

Following a single dose, median Tmax was approximately 2-3 hours. The mean AUC0-24 on Day 1 increased approximately 9 fold from 20 to 150 mg. The mean terminal elimination half-life on Day

1(T_{1/2}) was 3-7 hr. Despite the relatively short half-life on Day 1, accumulation was observed with daily dosing at doses \geq 60 mg, likely due to auto-inhibition of CYP3A4 mediated clearance pathways. Mean accumulation ratio (R_{acc}) ranged from 3 to 8 on Days 15 and 28. Since dose interruptions occurred frequently following continuous daily dosing of Infigratinib, PK parameters on Day 28 should be viewed with caution. The interpatient variability was high for Infigratinib.

Concentration data from active metabolites BHS697 (desethyl metabolite) and BQR917 (Noxide) was available across all cohorts. CQM157 (aniline metabolite) was analyzed in a few patients following Amendment 6 of the InfigratinibX2101 clinical protocol. In most patients, BHS697 and BQR917 were measurable at levels of ~5-50%, and <15% of parent exposure, respectively. Mean exposures on Day 1 (N=8) for CQM157 relative to Infigratinib varied across patients (3% -300%). CQM157 (N=4) did not appear to accumulate on daily dosing, whereas accumulation was observed for Infigratinib and metabolites BHS697 and BQR917. Please refer to Investigator's Brochure for more details.

2. Rationale

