2.3 Rationale for dose and regimen selection

Patients enrolled in this study will receive 125 mg qd of Infigratinib on a 3 week on (21 day) /1 week off (7 day) schedule in 28-day cycles. This dose level and regimen is based on experiences from the CInfigratinibX2101 trial.

The MTD/RP2D from the CInfigratinibX2101 study was identified as 125 mg administered once daily (qd) in continuous 28-day cycles. While dose levels of 100 mg qd and higher were tolerated by patients, the majority of the patients experienced reversible hyperphosphatemia, which led to study drug interruptions. An evaluation of the drug administration records for patients prior to receiving prophylactic phosphate-lowering therapy, indicated that the median time until first dose interruption was approximately 23 days and the median duration of interruption was 7 days. This observation led to the introduction of an expansion arm in the ongoing CInfigratinibX2101 study to evaluate the administration of 125 mg qd on a 3 week on (21 days) / 1 week off (7 days) schedule in 28-day cycles. To date, the majority of patients enrolled in this arm have completed their first cycle of therapy without hyperphosphatemia induced dose interruptions, while maintaining anti-tumor activity.

3. Objectives and endpoints

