4.1 Description of study design

This is a multi-center, open label, single arm phase 2 study evaluating Infigratinib anti-tumor activity in advanced or metastatic solid tumor patients with *FGFR* genetic alterations including gene fusions/translocations, point mutations, and insertions/deletions. Oral, monotherapy Infigratinib will be administered once daily for the first 3 weeks (21 days) followed by one week break of each 28-day cycle. Treatment period will begin on Cycle 1 Day 1 and will continue until disease progression, unacceptable toxicity, withdrawal of informed consent, or death. Patients will be evaluated for tumor response radiographically every 8 weeks until disease progression or discontinuation from study using RECIST v1.1.

As depicted in Figure 1, patient accrual for the current study will occur at The Ohio State University and through clinical sites from institutions that are members of the Oncology Research Information Exchange Network (ORIEN, <http://oriencancer.org/>). OSU is a founding member of ORIEN, which includes eighteen large academic hospital systems with patients who have consented to a common study that includes tumor profiling by next generation sequencing (whole exome and RNAseq), collection of clinical data, and re-contact for potential clinical trials offering therapies that match the genetic alterations in their cancers. Thus, ORIEN provides a mechanism for pre-screening to identify candidate patients with *FGFR* genetic alterations and can help accelerate patient accrual to this study.

Clinical subsites to be determined based on populations of *FGFR*+ patients and interest from ORIEN members. Additional non-ORIEN clinical sites may be identified as well. Regardless of prior research screening, all patients must have had CLIA-certified assay with requisite *FGFR* gene alterations. Additional subsites with active molecular testing for *FGFR* may also be recruited as a clinical subsite.

[figure not shown]

Figure 1. Study schema for phase 2 trial evaluating Infigratinib efficacy in patients with advanced *FGFR*-altered solid tumors with and without prior exposure to alternate *FGFR* inhibitor therapy.

Molecular Eligibility

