Worst Toxicity CTCAE v5.0 Grade (unless otherwise specified)	Recommended Dose Modifications any time during a cycle of therapy
Laboratory / Metabolic disorders	
Asymptomatic amylase and/or lipase elevation	
Grade 3 (> 2.0 - 5.0 x ULN with signs or symptoms; >5.0 x ULN and asymptomatic)
 
 • Hold dose of Infigratinib until resolved to CTCAE Grade \leq 2. • ↓ 1 dose level of Infigratinib 
For recurrent Grade 3 asymptomatic lipase or amylase elevation despite dose reduction, drug should be held and continuation of therapy should be discussed with the medical monitor following resolution to \leq Grade 2.

Grade 4 (>5.0 x ULN and with signs and symptoms)	
For any Grade 4 asymptomatic lipase or amylase elevation, drug should be held and continuation of therapy should be discussed with the medical monitor following resolution to \leq Grade 2.

	
Note: A CT scan or other imaging study to assess the pancreas, liver, and gallbladder should be performed as clinically indicated within 1 week of the first occurrence of any CTCAE \geq Grade 3 amylase and/or lipase.

Hyperphosphatemia	
Grade 1: Laboratory finding only and intervention not indicated	
Maintain dose level of Infigratinib and optimize phosphate lowering therapy as clinically indicated.

Grade 2: Noninvasive intervention indicated	
Maintain dose level of Infigratinib and optimize phosphate lowering therapy as clinically indicated.

Grade 3: Severe or medically significant but not immediately life-threatening; hospitalization or prolongation of existing hospitalization indicated	
Hold Infigratinib until resolved \leq Grade 2. Restart at same dose level with maximal phosphate binder dosing.

Grade 4: Life-threatening consequences; urgent intervention indicated (e.g. dialysis)	
Hold Infigratinib until resolved \leq Grade 2. Reduce one dose level dose level with maximal phosphate binder dosing.

	
It is recommended that phosphate binder dosing continues during Infigratinib dose interruptions for hyperphosphatemia and that serum phosphorus values be monitored frequently, e.g. every 2-3 days.

	
Phosphate binder dosing should be held during the week off Infigratinib therapy each cycle (Days 22-28) and during Infigratinib dose interruptions for non-hyperphosphatemia adverse events.

Worst Toxicity CTCAE v5.0 Grade (unless otherwise specified)	Recommended Dose Modifications any time during a cycle of therapy

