7.1 Study flow and visit schedule

Table 7 lists all of the assessments and indicates with an “X” the visits when they are performed. All data obtained from these assessments must be supported in the patient’s source documentation. The table indicates which assessments produce data to be entered into the database (D) or remain in source documents only (S) (“Category” column).

- Baseline imaging assessments can be conducted within 28 days prior to 1st day of study treatment.
- All other baseline/screening assessments must be performed within 21 days prior to 1st treatment.
- Baseline/screening assessments that are conducted within 3 days prior to 1st treatment can be used to satisfy the day 1 requirement. Every effort must be made to follow the schedule outlined in **Table 7**.

For all visits, there is a \pm 3-day window on assessments to take into account scheduling over weekends and holidays, if not explicitly specified otherwise. For post baseline imaging assessments, a \pm 7 day window is allowed, except for the first post baseline assessment (+7 day window permitted).

All assessments should be performed as outlined in **Table 7** and as clinically indicated.

Table 7: Visit evaluation schedule

	Category	Screening	Cycle 1				Cycle 2		Cycle 3		Subsequent cycles	End of study treatment	30-day follow-up (end of study)	Disease Progression follow-up every 8 weeks	Survival follow-up (every 4 months after EOT for 1 year)
Study Period			Treatment									EOT	Follow-up		
Day of Cycle		-28 to -1	1	8	15	21	1	15	1	15	1	≤14 days of decision to discontinue treatment			
Study Informed Consent (ICF)	D	X													
Demography	D	X													
Inclusion/exclusion criteria	D	X													
Relevant medical history/current medical conditions	D	X													
Diagnosis and extent of cancer	D	X													
Prior antineoplastic therapy	D	X													
Prior/concomitant medications	D	X	Continuous									X	X		
Physical examination	S	X	X	X	X	X	X	X	X	X	X	X			
Height	D	X													
Weight	D	X	X				X		X		X	X			
Vital signs	D	X	X	X	X	X	X	X	X	X	X	X			
Performance status	D	X	X				X		X		X	X			
Ophthalmic assessment	D	X			X		X		X		X	X			
Hematology	D	X	X	X	X	X	X	X	X		X	X			
Chemistry	D	X	X	X	X	X	X	X	X		X	X			
Coagulation	D	X	If clinically indicated												
Urinalysis (microscopic or macroscopic)	D	X	If clinically indicated												
Pregnancy test	D	X	X				X		X		X	X			

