7.2.2.7 Cardiac assessments

ECG evaluations will be conducted centrally. For all patients prior to the first administration of Infigratinib, a minimum of 3 sequential 12-lead ECGs, separated by at least 5-10 minutes, must be performed on Day 1 of Cycle 1. This is necessary to get an accurate baseline QTcF calculation. 12-lead ECGs are to be performed at the following time-points:

- At screening and/or baseline
- Cycle 1 Day 1: pre-dose and 2-hr post-dose, \pm 15 min. (3 sequential)
- Cycle 1 Day 15: pre-dose (3 sequential)
- All Subsequent cycles, day 1: pre-dose (3 sequential)
- At the end of treatment

Clinically significant abnormalities present when the patient signed informed consent should be reported on the Medical History eCRF page. Clinically significant findings must be discussed with the The Ohio State University Principal Investigator (Sponsor) prior to enrolling the patient in the study. New or worsened clinically significant findings occurring after informed consent must be recorded on the AE eCRF page.

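### After Cycle 2 Day 15, every chemistry panel scheduled to a cycle day follows the drug-free week, so later-cycle values may understate on-drug phosphate and cannot show whether it is controlled on treatment

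*Combined protocol and SAP*

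**What the plan says.** Under Section 4.1 the drug is "administered once daily for the first 3 weeks (21 days) followed by one week break of each 28-day cycle". Section 7.2.2.6 leaves the timing of chemistry to Table 7: "Clinical chemistry tests are to be performed by the local laboratory according to the visit schedule outlined in" that table. Table 9 places phosphate, calcium, creatinine and lipase in that panel.

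The day header of Table 7 reads "28 to -1 1 8 15 21 1 15 1 15 1": screening, Cycle 1 Days 1, 8, 15 and 21, Cycle 2 Days 1 and 15, Cycle 3 Days 1 and 15, then Day 1 of later cycles. An end-of-treatment column follows. The chemistry row reads "Chemistry D X X X X X X X X X X", which is ten marks for eleven visit columns. The blank cell is Cycle 3 Day 15. That visit does take place: physical examination and vital signs are marked, and blood is drawn for ctDNA (Table 7, Section 7.2.3.2).

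On phosphate, Sections 6.1.2 and 6.3.1 call for phosphate-lowering treatment to be started prophylactically and adjusted for as long as the drug is given. Table 6 adds: "Phosphate binder dosing should be held during the week off Infigratinib therapy each cycle (Days 22-28".

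For ECGs, Section 7.2.2.7 sets Cycle 1 Day 1 before the dose and 2 h after it, Cycle 1 Day 15 before the dose, then "All Subsequent cycles, day 1: pre-dose (3 sequential", and end of treatment.

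Section 10.5 describes laboratory values over time and by grade. It does not distinguish samples taken on drug from samples taken after the break.

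**The concern.** Hyperphosphatemia is the main on-target toxicity. Section 1.2.1.4.1 reports it in 82.5% of patients in the phase 2 cholangiocarcinoma study, Grade 3 or 4 in 15.9%. The week off exists because of it: Section 2.3 reports that before prophylactic phosphate-lowering therapy "the median time until first dose interruption was approximately 23 days and the median duration of interruption was 7 days". Day 1 is therefore a point by which phosphate has had time to fall.

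If all later scheduled panels come from that point, they describe phosphate off drug and off binder. They do not describe it under treatment. Two things are at stake. Secondary objective 2 is to characterise safety and tolerability, and a fall in phosphate from Cycle 3 onward could reflect only the change in sampling time. In addition, the plan asks for phosphate-lowering therapy to be adjusted throughout dosing, but from late Cycle 2 it schedules no on-drug measurement on which to base that.

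**Working it through.** The plan states no figure to reproduce. The check covers sampling times, residual drug and share of dosing time.

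**Sampling times (Table 7).**
- On drug after at least one week of dosing: Cycle 1 Days 8, 15 and 21; Cycle 2 Day 15.
- After the break: Day 1 of Cycle 2, Cycle 3 and every later cycle.
- Not tied to a cycle day: end of treatment.

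From Cycle 4 the table has only a Day 1 column, so the later-cycle point does not depend on how the Cycle 3 Day 15 cell is read.

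**Gap.** From the Day 21 dose to the next Day 1 (Day 29) is 8 × 24 = 192 h.

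**Residual drug at the stated half-life.** Section 1.2.1.2.3 gives 3-7 h after a single dose. Residual = 0.5^(192/t):
- t = 3 h: 64 half-lives, about 5 × 10⁻²⁰.
- t = 7 h: 27.4 half-lives, about 6 × 10⁻⁹.

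**Residual drug from accumulation.** The same section says the mean accumulation ratio "ranged from 3 to 8 on Days 15 and 28". Assuming one compartment and 24 h dosing, R = 1/(1 − e^(−24k)), so e^(−24k) = 1 − 1/R, and the residual after eight days is (1 − 1/R)⁸:
- R = 3: effective half-life 41 h, residual (2/3)⁸ = 3.9%.
- R = 8: effective half-life 125 h, residual (7/8)⁸ = 34%.

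The 34% is an upper bound, because it holds the inhibition of clearance constant through the week off. At the early edge of the ±3-day visit window (120 h) the figures are (2/3)⁵ = 13% and (7/8)⁵ = 51%.

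**Share of dosing time, six cycles.**
- Total: 6 × 21 = 126 dosing days.
- After Cycle 2 Day 15: 6 + 4 × 21 = 90, or 90/126 = 71%.
- With a panel at Cycle 3 Day 15: 6 + 3 × 21 = 69, or 69/126 = 55%.

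**ECG, same one-compartment model.** The pre-dose level at steady state is 1 − 1/R of the peak: 67% at R = 3 and 88% at R = 8. Relative to the first-dose peak it is R − 1, that is 2 to 7 times. The Cycle 1 Day 15 pre-dose ECG is therefore taken at substantial exposure in this model.

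**The case against.** The strongest reply is that the schedule is a deliberate taper. Sampling is dense early, when interruptions are expected. Hematology is also blank at Cycle 3 Day 15, and a Day 1 panel has a clear use before redosing. Table 7 and Section 7.2.2.7 agree with each other. Tests may be added when clinically indicated (Sections 7.1, 7.2.2.6). Table 6 recommends phosphorus every 2-3 days during interruptions for hyperphosphatemia, and Section 6.2.2 requires weekly follow-up after an interruption for a significant laboratory value.

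Much of this stands. Early on-drug sampling is adequate, and the blank cell is not proof of an oversight. But the added tests are either discretionary or follow detection, so they do not supply routine on-drug values in later cycles.

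The reply also rules out several stronger readings that a reader might infer:

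- *That later laboratory toxicity will be understated.* The documents give neither onset by cycle nor recovery times for phosphate, calcium, creatinine or lipase. A median interruption of 7 days means that about half lasted at least that long, and interruption length is not recovery time. Table 6 itself provides for creatinine and calcium events that take more than 7 days to resolve. Holding the binder also acts on Day 1 phosphate, in the upward direction.
- *That the Table 6 rules would rarely be triggered.* Table 6 grades hyperphosphatemia by the intervention needed, without a phosphate threshold, and keeps the dose at Grades 1 and 2.
- *That a clean QT result would be uninformative.* The only post-dose ECG does follow the first dose. However, the Cycle 1 Day 15 ECG is on drug, an end-of-treatment ECG and ECGs triggered under Table 6 exist, and Section 1.2.1.4.1 reports no effect on QTc.

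**Conclusion.** The point holds for chemistry in later cycles, and above all for phosphate. After Cycle 2 Day 15, no panel tied to a cycle day is scheduled later in the dosing block than a Day 1 that follows the break. Values from these visits may understate on-drug phosphate and cannot show whether it is controlled on treatment. An apparent later-cycle improvement in the Section 10.5 tables could not be separated from the change in sampling time.

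The 71% assumes six full cycles without interruption and measures dosing time only. It should not be read as the proportion of events missed. The residual-drug range of about 0% to 34% depends on which pharmacokinetic figure is used. The accumulation ratios come from the phase 1 study, and Section 1.2.1.2.3 itself advises caution with Day 28 parameters. Drug level is also only a proxy for phosphate. The ECG timing is a minor point. This is worth correcting because it bears on a secondary objective and costs little; it does not affect the response-rate analysis.

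**What to change.** 1. In Section 10.5, summarise laboratory values and grades separately for on-drug and post-break samples, and state that scheduled values from Cycle 3 onward are post-break. Unscheduled samples can be classified from sampling and dosing dates. This changes the analysis only.
2. Reconcile the chemistry row of Table 7 with the 3-weeks-on, 1-week-off regimen, with Sections 6.1.2 and 6.3.1, and with Table 6. One option is the existing Cycle 3 Day 15 visit, where blood is already drawn. That alone would lower the 71% to 55% and leave Cycle 4 onward unchanged. Any further on-drug timing, and any change to ECG timing in Section 7.2.2.7, is for the sponsor to decide.

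The cost is a short amendment and, if that option is taken, one local panel at an existing visit. Reported laboratory toxicity may look less favourable.
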